6.2. Current Treatment and Unmet Medical Need

Medical treatment for CHI is focused on chronic therapies to avoid hypoglycemia, as well as on rescue therapy during acute episodes of severe hypoglycemia. Available medical therapies (mainly diazoxide, octreotide, or glucagon alone or in combination with glucose infusion) are often inadequate and accompanied by inability to control PG, as reflected in a large proportion of patients requiring sub-total pancreatectomy.^{4,5,6} With the exception of surgery for focal CHI, which is curative in the vast majority of patients, sub-total pancreatectomy for diffuse CHI has substantial inadequacies. A recent retrospective chart review⁷ showed that 60% of patients who underwent near-total pancreatectomy had persistent hypoglycemia after surgery. Moreover, 96% had developed insulin-dependent diabetes within 11 years after surgery.

First-line medical treatment of CHI is diazoxide, which is the only EU- and US-approved drug for treatment of hyperinsulinemic hypoglycemia. Diazoxide acts to open K_{ATP} channels of the pancreatic β -cells, thereby inhibiting insulin secretion. Unfortunately, many patients with CHI are resistant to diazoxide because of mutations in the genes encoding the K_{ATP} channel of the pancreatic β -cells.⁶ For those who respond to diazoxide treatment, the more common side effects comprise hypertrichosis, fluid retention, and gastrointestinal (GI) symptoms; however, side effects are usually not severe. In diazoxide nonresponders, second-line (and off-label) treatment is a somatostatin analog (octreotide or lanreotide [long acting]), which (among other effects) inhibits secretion of insulin and glucagon from the pancreas and suppresses GLP-1 secretion. Factors that limit their use comprise tachyphylaxis, as well as possible side effects, including necrotizing enterocolitis, gallstones, and hepatitis.⁶

The glycogenolytic effect of glucagon and its ability to increase PG levels has been confirmed in children with CHI or neonatal hypoglycemia.^{8,9} Administration of marketed glucagon (intravenous [IV] or subcutaneous [SC] injection) is often used in the diagnostic phase of CHI to

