13.4.3.3. Secondary and Other Efficacy Analyses

Part 1

A mixed-model regression approach will be used to analyze the weighted mean IV GIR over 48-hour treatment period during Part 1 (dasiglucagon or placebo administration) similar to the primary analysis for the primary endpoint.

A generalized estimating equation (GEE) method with a logit link function will be used to analyze the weighted mean IV GIR below 10 mg/kg/min in the last 12 hours of each treatment period during Part 1 (yes/no) (dasiglucagon or placebo administration) to account for repeated observations in patients. In case of non-convergence, a Mc Nemar test will be used.

No sensitivity analysis will be used on these endpoints.

Part 2

Due to the potential impact of pancreatectomy on the secondary endpoints during Part 2, any endpoint assessment after pancreatectomy will not be included in the primary analyses

(endpoints set to missing after pancreatectomy). Sensitivity analyses will be run on those endpoints including all assessments in the descriptive analyses.

For Part 2 efficacy endpoints, continuous and categorical endpoints will be presented using summary statistics or frequencies, respectively; no formal testing will be performed. For the time to complete weaning off IV GIR, the time to actual hospital discharge and the time to pancreatic surgery, Kaplan-Meier curves will be produced.

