8.3.1. Primary Analyses for Secondary Endpoints

Part 1 (Day 1 to 4, for each 48-hour treatment period)

- Weighted Mean IV GIR for each 48-hour treatment period during Part 1 (dasiglucagon or placebo administration). This endpoint will be analyzed using the same mixed-model regression approach as the one used for primary endpoint and removing IV GIR data that are not valid for site 101. No sensitivity analysis on this endpoint.

- Weighted Mean IV GIR below 10 mg/kg/min in the last 12 hours of each treatment period during Part 1 (yes/no) (dasiglucagon or placebo administration). For this analysis a generalized estimating equation (GEE) method with logit link function will be used using below program and removing IV GIR data that are not valid for site 101.

```
PROC GENMOD;  
  CLASS PATIENT PERIOD TRT;  
  MODEL OUTCOME= PERIOD TRT / LINK=LOGIT DIST=BINOMIAL ;  
  REPEATED SUBJECT=PATIENT/ WITHIN=PERIOD TYPE=CS;  
  LSMEANS TRT / ILINK CL EXP DIFF;  
  ESTIMATE "DASIGLUCAGON versus PLACEBO" TRT 1 -1 ;  
RUN;
```

Part 2 (Day 5 to 25, assessed from the start of treatment in part 2)

If patient needs a pancreatectomy, this will occur only during the Part 2 of the study. If pancreatectomy was done before randomization, it will not be taken into account. Only patients with pancreatectomy during the study will have censored values.

The evaluation of the Part 2 endpoints will then be impacted by pancreatectomy. To be able to assess only treatment effect as primary analysis the following rules will be applied:

- SMPG-detected episode, Carbohydrates administrated, CGM-detected episode, CGM percent time endpoint and extent of hypoglycemia will be set to missing after pancreatectomy (whatever percentage of pancreatectomy).
- Time to complete weaning off IV GIR and time to actual hospital discharge will be censored at time of pancreatectomy (whatever percentage of pancreatectomy).

Following endpoints will be described by week and over the three weeks period.

- Time to complete weaning off IV GIR. Only patient without complete weaning off IV GIR at start of Part 2 will be included in this analysis. Kaplan-Meier estimates will be given for each of the three weeks treatment period.
- Rate of SMPG-detected hypoglycemia episode, defined as number of hypoglycemic events (PG <70 mg/dL or 3.9 mmol/L).
- Rate SMPG-detected Clinically significant hypoglycemia episode, defined as number of events <54 mg/dL (3.0 mmol/L).

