- Time to actual hospital discharge. Kaplan-Meier estimates will be given for each of the three weeks treatment period.
- Time to pancreatic surgery (sub-total or total pancreatectomy, cutoff 95% or more).
- Total amount (g) of carbohydrates administered (regardless of route) per day, together with amounts (g) of carbohydrates administered per day:
 - via IV glucose infusion or bolus (not as part of total parenteral nutrition),
 - as part of total parenteral nutrition (if applicable),
 - via oral route, and
 - via NG tube or gastrostomy.
- CGM percent time in range 70-180 mg/dL (3.9-10.0 mmol/L).

- CGM percent time in hypoglycemia (<70 mg/dL or 3.9 mmol/L).
- CGM percent time in clinically significant hypoglycemia (<54 mg/dL or 3.0 mmol/L).
- Rate of CGM-detected hypoglycemia episodes, defined as number of episodes <70 mg/dL (3.9 mmol/L) for 15 min or more.
- Rate of CGM-detected clinically significant hypoglycemia episodes, defined as number of episodes <54 mg/dL (3.0 mmol/L) for 15 min or more.
- Extent of hypoglycemia (area over the glucose curve [AOC_{glucose}] below 70 mg/dL [3.9 mmol/L]) as measured by CGM. Extent of hypoglycemia will be presented in mmol/L and mg/dL.
- Extent of clinically significant hypoglycemia (AOC_{glucose} below 54 mg/dL [3.0 mmol/L]) as measured by CGM. Extent of hypoglycemia will be presented in mmol/L and mg/dL.
- CGM percent time in hyperglycemia (>180 mg/dL or 10.0 mmol/L).

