8.3.2. Sensitivity Analyses for the Key Secondary Endpoints

In addition, a sensitivity analysis will be performed for all secondary endpoints related to Part 2 not applying any missing rule when pancreatectomy (whatever percentage of pancreatectomy). is performed. Time to pancreatic surgery will not be included in this sensitivity analysis as not impacted by missing rules.

As paracetamol is a prohibited medication that can impact CGM endpoint evaluation for Dexcom G4 users a sensitivity analysis on CGM percent time in hypoglycemia (< 70mg/dL) will be run excluding following CGM data:

- For each use of paracetamol (from concomitant medication form preferred term =”PARACETAMOL”) for G4 users exclude CGM data if paracetamol start date <= CGM date <= paracetamol end date + 4 hours

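### The Part 2 Kaplan-Meier estimates of weaning and discharge censor at pancreatectomy, and no planned analysis gives the proportion weaned or discharged on dasiglucagon without surgery

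*SAP*

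**What the plan says.** - **Censoring rule.** SAP 8.3.1 (Part 2) introduces its pancreatectomy rules with "To be able to assess only treatment effect as primary analysis the following rules will be applied". For the two time-to-event endpoints the rule is: "Time to complete weaning off IV GIR and time to actual hospital discharge will be censored at time of pancreatectomy". It applies to a resection of any extent.
- **Protocol.** Section 13.4.3.3, identical in the German and non-German versions, states the general principle that "any endpoint assessment after pancreatectomy will not be included in the primary analyses". It names the estimator: "the time to actual hospital discharge and the time to pancreatic surgery, Kaplan-Meier curves will be produced". The explicit censoring rule for weaning and discharge stands only in the SAP.
- **Estimator.** Kaplan-Meier is the only one named. For discharge, SAP 8.3.1 says "Time to actual hospital discharge. Kaplan-Meier estimates will be given for each of the three weeks treatment period", and it says the same for weaning. Neither document plans a cumulative incidence or a surgery-as-failure analysis.
- **Sensitivity analysis.** Under SAP 8.3.2, "a sensitivity analysis will be performed for all secondary endpoints related to Part 2 not applying any missing rule when pancreatectomy" is performed. Time to surgery is exempt.
- **Time to pancreatic surgery.** This is a separate Kaplan-Meier endpoint, but SAP 6.1.7 and 8.3.1 count only resections of 95% or more.
- **Why surgery happens.** Protocol 6.2 links surgery to poor medical control, "as reflected in a large proportion of patients requiring sub-total pancreatectomy". It sets focal disease apart: "With the exception of surgery for focal CHI, which is curative in the vast majority of patients".

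**The concern.** An infant operated on before weaning can no longer wean on dasiglucagon without surgery. Censoring treats that infant as if weaning were still possible and passes its weight to the infants still at risk. The resulting percentage can exceed the share of infants who reached the goal on drug alone.

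Weaning from IV glucose and discharge are what Part 2 is designed to bring about (Protocol 8.1 and 10.2). Part 2 has no control arm, so the percentages will be read at face value. The two planned versions answer other questions: one asks what would have happened without surgery, the other what happened with or without it.

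There is also a gap at the edges. A resection below 95% censors weaning and discharge but is not an event in time to pancreatic surgery. It is therefore an event in no primary time-to-event analysis.

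**Working it through.** **Inputs.** N = 12 (SAP 3.2) and 21 days of single-arm follow-up (Protocol 8.1). The documents state no rate of pancreatectomy, weaning or discharge, so there is no planned figure to reproduce. All counts and timings below are assumptions.

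**Step 1: direction.** With d weanings among n at risk at each time:

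- 1-KM = sum of S_KM(t-) × d/n, where S_KM falls only at weanings.
- Aalen-Johansen cumulative incidence = sum of S_all(t-) × d/n, where S_all falls at weanings and at operations.

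S_all is never above S_KM, so 1-KM is never below the cumulative incidence. It is above it whenever an operation precedes a later weaning. This does not depend on the reason for surgery.

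**Step 2: size, 12 infants, 6 weaned, s operated, the rest followed to day 21 without weaning.** The cumulative incidence is 6/12 = 50% throughout.

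- All operations before any weaning: 1-KM = 6/(12 - s).
- Operations after the third weaning: 1-KM = 1 - (9/12) × (6 - s)/(9 - s).
- Operations after the last weaning: 1-KM = 6/12.

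| Operated (s) | Early | Midway | After last weaning |
|---|---|---|---|
| 1 | 54.5% | 53.1% | 50.0% |
| 2 | 60.0% | 57.1% | 50.0% |
| 3 | 66.7% | 62.5% | 50.0% |
| 4 | 75.0% | 70.0% | 50.0% |

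An extreme case: 8 weaned and 4 operated, early or midway. The last infant at risk weans, so 1-KM is 100% against 8/12 = 66.7%.

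SAP 8.3.1 leaves infants already weaned at the start of Part 2 out of the weaning analysis. The risk set may then be below 12, and each operation can weigh more.

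**Step 3: the planned sensitivity analysis.** It keeps operated infants at risk and counts later weaning.

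- 6 weaned on drug, 2 operated, both wean later: (6 + 2)/12 = 66.7%.
- 6 weaned on drug, 2 operated, neither weans: 6/12 = 50%, which equals the cumulative incidence.

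**Step 4: against the SAP's no-surgery target.** A simulation of 400,000 infants over 21 days assumed that 40% never wean on drug, that the others wean after an exponential time with mean 7 days, and that operations fall uniformly between days 3 and 18. The true no-surgery proportion is 0.6 × (1 - e^-3) = 57.0%.

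| Who is operated on | Operated before weaning | 1-KM | Weaned without surgery |
|---|---|---|---|
| Only infants who would never wean | 10% | 59.3% | 57% |
| Only infants who would never wean | 20% | 62.7% | 57% |
| Unrelated to response | 11.3% | 57.1% | 54.4% |
| Unrelated to response | 16.8% | 57.1% | 53.2% |

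Against its own target, the censored curve is unbiased when surgery is unrelated to response. It is about 2 to 6 points too high when only non-responders are operated on.

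**The case against.** The strongest reply is that the SAP chose a different target. It wants the drug effect undisturbed by surgery, and for that target censoring is a recognised approach. Much of the gap in step 2 is then a difference between two questions. This stands: 50% is the right answer only to the question of success on drug without surgery. What remains is that the SAP does not state the assumption its target needs, and no analysis addresses the other question.

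A reader might infer that the censoring is always driven by treatment failure. The documents do not support that. The rule covers any resection, and Protocol 6.2 describes focal surgery as usually curative. Focal patients are expected: exclusion criterion 15 allows imaging to diagnose focal disease, and SAP 7.3 plans to describe it. The focal/diffuse mix is not given, so how informative the censoring is cannot be established.

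A reader might also infer that both planned estimates are too high whenever surgery occurs. They are not. The censored curve shows no gap if surgery follows the last weaning. The sensitivity version shows none if operated infants never wean or go home afterwards. Where they do, it is still a legitimate treatment-policy estimate.

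Finally, the consequence is limited. Part 2 endpoints carry no inference (SAP 8.3), all data are listed (SAP 6.1.8), and with about 12 infants a reader could count successes by hand. This lowers the stakes, but a count from listings does not replace a labelled estimate in the report.

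**Conclusion.** The point holds in a limited form. Kaplan-Meier censored at pancreatectomy does not estimate the proportion weaned or discharged on dasiglucagon without surgery. For that quantity it is too high whenever an operation precedes a later weaning or discharge. For the SAP's no-surgery target it is valid only if surgery is unrelated to the chance of weaning. That is doubtful mainly in diffuse disease and need not fail for focal surgery.

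The size cannot be derived from the documents. Under the assumed counts with 6 of 12 weaned, the gap is 3 to 25 points for one to four early or midway operations, and zero if none precedes a later weaning. The documents do not support a claim that the trial's main conclusion is at risk: the Part 1 primary endpoint, the testing hierarchy and the power are untouched.

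**What to change.** In SAP 8.3.1:

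1. Add the Aalen-Johansen cumulative incidence of complete weaning and of discharge, by week and over the three weeks, with pancreatectomy of any extent as the competing event.
2. Report the number of operations by focal or diffuse disease and by extent of resection, so that those below 95% are visible.
3. Keep the censored Kaplan-Meier, labelled as a hypothetical (no-surgery) estimate that assumes non-informative surgery.
4. Keep the version that ignores surgery as the sensitivity analysis in 8.3.2.

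The cost is a few SAP sentences, a standard procedure option and one small table. No new data should be needed: the SAP already plans to describe focal disease and must know the extent of resection to apply its 95% cutoff. The downside is a possibly less favourable curve that also reflects local surgical decisions and counts curative focal surgery as a competing event. That is why it should stand beside the censored curve rather than replace it.

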8.3.2. Sensitivity Analyses for the Key Secondary Endpoints

In addition, a sensitivity analysis will be performed for all secondary endpoints related to Part 2 not applying any missing rule when pancreatectomy (whatever percentage of pancreatectomy). is performed. Time to pancreatic surgery will not be included in this sensitivity analysis as not impacted by missing rules.

As paracetamol is a prohibited medication that can impact CGM endpoint evaluation for Dexcom G4 users a sensitivity analysis on CGM percent time in hypoglycemia (< 70mg/dL) will be run excluding following CGM data:

- For each use of paracetamol (from concomitant medication form preferred term =”PARACETAMOL”) for G4 users exclude CGM data if paracetamol start date <= CGM date <= paracetamol end date + 4 hours

8.4. Other Efficacy Analysis

8.4.1. CHI Related Hospitalization

The frequencies and percentage of patients with admissions/emergency department visits for hypoglycemia, hospitalizations due to CHI or CHI-related events, visits to health care providers (family doctor, specialists, etc.) caused by CHI or CHI-related events and need for home visits by paramedics due to hypoglycemia will be summarized by week for Part 2.

Additionally, number and length (in days) of hospitalizations due to CHI, number of visits to health care providers (family doctor, specialists, etc.) caused by CHI or CHI-related events, and number of home visits by paramedics due to hypoglycemia will be summarized by week for Part 2 and for the patients in FAS.

9. Safety and Tolerability Analysis

Safety assessments will include the evaluation of AEs, clinical laboratory assessments (hematology, biochemistry, and ADAs), vital signs, physical examinations; electrocardiograms (ECGs), echocardiography, and local tolerability issues. No formal inferential analyses will be conducted for safety variables, unless otherwise specified.

All safety analyses will be summarized by treatment received within treatment period and part also by active treatment (Dasiglucagon pooling data of part 1 and part 2) and by study visit, if applicable.

9.1. Adverse Events

An AE is any untoward medical occurrence in a clinical trial patient administered a medicinal (investigational or non-investigational) product and which does not necessarily have a causal relationship with this treatment. An AE can therefore be any unfavorable and unintended sign (including an abnormal laboratory finding), symptom, or disease temporally associated with the use of a product, whether or not related to the product. A treatment-emergent AE (TEAE) is defined as an AE with an onset at the time of or following the start of treatment with the trial drug (Dasiglucagon or Placebo) through the Follow-up Visit or Early Termination Visit, whichever occurs first. An AE will be assigned to the treatment period the AE started.

The causal relationship of the AE to the study drug is determined by the investigator as Not Related, Unlikely, Possible, and Probable. These will be mapped to Unrelated (*Not Related* or *Unlikely*) and Related (*Possible* or *Probable*) for summarization purposes. Any missing relationship will be mapped to “Related”.

Adverse event severity grades are reported as mild, moderate, or severe.

Each patient will be counted only once within each summation level system organ class (SOC) and preferred term (PT). The summary will be presented in descending order of frequency of SOC and then PT within SOC based on overall patients.

The incidence of TEAEs will be summarized with frequencies and percentages for patients in Safety Set (including number of TEAEs occurring, as well as rate of events [number of events /

100 years of exposure in each part]), by part and treatment group and also overall for Dasiglucagon group for the following:

- SOC and PT
- SOC, PT, and severity
- SOC, PT, and relationship to study drug
- SAEs by SOC and PT

9.1.1. Adverse Events Leading to discontinuation of study drug

A summary of incidence rates (frequencies and percentages) of TEAEs leading to discontinuation of study drug, by part and treatment group, overall for Dasiglucagon group, SOC, and PT will be prepared for patients in Safety Set. No inferential statistical tests will be performed.

A data listing of TEAEs leading to discontinuation of study drug will also be provided displaying details of the event(s) captured on the CRF.

9.1.2. Deaths and Serious Adverse Events

Any deaths that occur during the study will be listed.

Serious TEAEs and Related Serious TEAEs will be listed and also tabulated by SOC and PT and presented by part and treatment group and overall for Dasiglucagon group.

9.1.3. Other Significant Adverse Events

Four types of AEs of special interest (AESI) are collected in this study. They are:

- Risk of liver injury
- Neurological events,
- Suspicion of necrolytic migratory erythema,
- Post-Dose Hemodynamic Changes

All Treatment Emergent AESI types occurring in at least 1 patient will be presented.

Incidence of Treatment Emergent AESI will be summarized by frequencies and percentages by part, treatment group and overall for Dasiglucagon group for patients in Safety Set by the following:

- AESI type, SOC, PT
- AESI type, SOC, PT, and relationship to the study drug

Additional information describing each AESI type, captured separately from date in the AE CRF, will be listed.

9.2. Clinical Laboratory Evaluations

Samples for hematology and chemistry will be collected at the Screening and Day 6, Day 25 and Follow-up.

Descriptive summaries of observed and changes from baseline values will be presented for clinical laboratory values by study visit and treatment group within part and also overall for the Dasiglucagon group.

Shifts from baseline for clinical laboratory values below, within, or above the normal range will be provided for hematology and chemistry results.

Frequencies of clinically significant abnormal laboratory values for hematology and chemistry results will be presented by study visit and treatment group within part and also overall for the Dasiglucagon group.

Laboratory values that are outside the normal range will also be flagged in the data listings, along with corresponding normal ranges. Any out-of-range values that are identified by the investigator as being clinically significant will also be shown in a data listing.

Immunogenicity data will be analyzed descriptively from data at baseline, Day 25, and Follow-up. No statistical tests are planned. Baseline ADA-positive patients will be calculated as a percentage of the total number of patients whose baseline samples were tested for ADA. Overall ADA incidence, the combined results of treatment induced, and treatment boosted ADA-positive patients, will be calculated as a percentage of the total number of evaluable patients, excluding baseline positive patients without any samples available after drug administration. Titers will be reported as median and interquartile range. Antidrug antibodies will be listed.

